Demographic and Baseline Characteristic Subgroups	
 • Age: 
 ○ <35; 35-<50; ≥50 (for statistical modelling on efficacy analysis of PK/PD and health outcome, the first two groups will be consolidated, i.e. <50, ≥50) 
For the Table of summary of demographic characteristics only, the following age group should also be presented: ≤18, 19-64, ≥65 (FDAAA requirement) 18-64, 65-84, ≥85 (EMA requirement)
 • Race: 
 ○ White; Non-White ○ Black/ African American; Non- Black/ African American • Country 
 ○ Argentina ○ Mexico ○ Australia ○ Canada ○ France ○ Germany ○ Italy

Category	Covariates and / or Subgroups
	
 ○ Korea, Republic of ○ Russian Federation ○ South Africa ○ Spain ○ Sweden ○ United States ● Baseline viral load: 
 ○ <50; ○ ≥ 50 copies/mL. ● Baseline CD4+ cell count: 
 ○ <200; ○ 200 to <350; ○ 350 to <500; ○ ≥ 500 cells/mm³. ● Derived Baseline Centres for Disease Control and Prevention (CDC) category: 
 ○ Stage I ○ Stage II ○ Stage III
EMA Subgroup Category 3:	
Additional subgroup/covariates for PK/PD efficacy analysis	
 ● Last CAB/RPV Trough PK concentration (i.e. pre-dose PK concentration wk48) ● Week-8 CAB/RPV Trough PK concentration (i.e. pre-dose PK concentration at nominal visit of Week 8) 
Dichotomized into two subgroups:
 
≤ first Quartile vs > first quartile,
 
≤ Median vs > Median,
 
The Concentration will be treated as continuous variable in logistic regression modelling analysis (i.e. the concentration data will be log₂ transformed in this analysis so that, for assessing the effect, one unit increase of the point estimate of log₂ PK concentration is equivalent to ‘doubling the concentration’ in the original value).
 
If pre-dose PK concentration at wk48 is missing, then last pre-dose PK concentration prior to WK48 will be used
 
 ● BMI (<30, ≥ 30 kg/m²) at Baseline

Category	Covariates and / or Subgroups
	
 • Length of Injection Needle (<2, ≥2 inch) For PK/PD efficacy analysis, length of injection needle at Week 4B will be used.

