9.1.2. Planned Pharmacokinetic statistical analysis

Planned PK statistical analysis
Steady state concentration
Endpoints

 • log_e-transformation of the Trough/Pre-dose plasma concentrations (CAB/RPV) on Week 16-48
Covariates

 • Study Week
Data Handling

 • All data remains as is (observed).
Model Specification

 • A mixed effects ANOVA model will be fitted with Week (continuous variable) as a fixed effect and subject as a random effect for each analysis separately. The Kenward & Roger (KR) degrees of freedom approach will be used. The coefficient for the slope of the day effect on the log_e-scale will be used to evaluate steady state for each drug (CAB/RPV). The 90% confidence intervals for the slope for each treatment will be calculated. If it does not appear that steady-state has been demonstrated, early weeks (e.g. Week 16, 20, 24, etc...) results will be dropped

Planned PK statistical analysis
and the analysis repeated.
Model Checking & Diagnostics

 The Steady state will be claimed (the coefficient for the slope of the Week effect on the (natural) log scale was close to 0 or the 90% CI for the slope estimate included zero. If steady-state is not demonstrated, concentrations from early weeks (e.g. Week 16, 20, 24, etc...) dropped in sequence and the analysis repeated until either steady state shown or only two timepoints remain.
Model Results Presentation

 The coefficient for the slope of the day effect on the \log_e-scale, its Standard error and 90% interval will be presented.
Population PK Analysis
A population-based PK analysis will be done under separate Population-PK Reporting and Analysis Plans.
Exposure - antiviral activity analysis
Endpoints
Snapshot 'HIV-1 RNA \geq 50' at Week 48
Covariates
Randomisation strata (sex at Birth and baseline ART third agent class), demographic and Baseline characteristics (age <50 vs \geq 50, race, baseline CD4, baseline viral load, and baseline CDC subgroups), and additional subgroup/covariates for PK/PD efficacy analysis (last CAB/RPV trough concentration, CAB/RPV trough concentration at nominal visit of Week 8, Baseline BMI, length of injection needle). Please see details for defining these subgroups/covariates in Section 5.4.2.
Data Handling

 All data remains as is (observed).

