Model Specification
Logistic regression will be used to exam the correlation between the endpoint (Snapshot 'HIV-1 RNA \geq 50') at Week 48 and the covariates/subgroups. CAB/RPV trough concentration will be included in the models as continuous variables. This logistic regression analysis will be performed for each covariate, separately (univariate analysis), and will also be performed with one multivariate analysis using Backward stepwise selecting approach to identify the covariates potentially affecting virologic response.
Model Checking & Diagnostics
For the multivariate analysis, a logistic regression model that best predicts the dependent variable (i.e. 'HIV-1 RNA \geq 50') from the independent variables (i.e. covariates/factors with $P < 0.15$ from univariate analysis) will be determined using the backward stepwise selecting approach. The last trough and Week-8 trough PK concentrations will be logarithmically transformed with base of 2. The analysis will start with all covariates in the model and remove a covariate with the largest p-value (i.e. the least statistically significant) each time and continue until the stopping rule is reached

Planned PK statistical analysis
when all remaining covariates have p-value <15%.
Model Results Presentation

 The odds ratio, 95% confidence interval, and P value will be presented. Estimated effect represents the change in log odds for a two-unit increase in the pk concentration

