13.6.5. Pharmacokinetic

This document is intended for planning analysis of PK concentration data only. Population pharmacokinetics and identification of important determinants of variability will be described in a separate document.

Plasma CAB and RPV concentration-time data

Plasma samples for determination of CAB and RPV concentration will be collected throughout the Maintenance and Extension Phases of the study. Additional samples will be collected for storage during the Long-Term Follow-Up Phase.

Concentration values below the lower limit of quantification (NQ) will be imputed as zero for summary statistics (R&D Guideline: Non-Compartmental Analysis of Pharmacokinetic Data, GUI_51487 (3.0)) and will be denoted as "NQ" in concentration listings.

Evaluable concentration

PK concentration will be summarized in two ways: ‘all data’ without regard to timing relative to scheduled time and ‘evaluable data’.

The ‘evaluable data’ are from the samples that met sample collection window criteria. Sampling windows are set relative to the previous dose as follows:

- 1-5 hours for 2-hour post dose samples;
- ± 3-10 days post last injection for 1-week post injection visits;
- ±4 day for pre-dose sample.
- Samples impacted by dosing errors (wrong dose) or oral bridging will also be excluded

Timepoint	Evaluable window	For Programming:
PRE-DOSE: WK4B/56B only	20-28 hrs after last oral dose taken and the last 3 oral doses administered properly	20 hrs ≤ Days Since Last Oral Dose ≤ 28 hrs and the last 3 oral doses administered on the three consecutive days prior to WK4B/56B.
2-HR-POST:	1-5 hrs	1 hrs ≤ Hours Since Last Injection Dose ≤ 5 hrs
1-WK-POST:	3-10 days post last injection	3 d ≤ Days Since Last Dose ≤ 10 d
PRE-DOSE:	±4 days	24 d ≤ Days Since Last Dose ≤ 32d

Relative Time is calculated relative to the date and time of last previous dose. For example, if the time of the last previous dose (e.g. oral lead-in/oral-bridging) is missing, then the relative time for pre-dose PK sample will be set to missing and the sample will not be considered ‘evaluable’.

If a pre-dose sample is collected on the same day as the first dose of oral bridging, and the time of the first dose (not recorded in eCRF) is confirmed to be ‘after’ the collection of pre-dose sample (by medical monitor or Data querying), then this PK sample will not be impacted by the oral bridging.

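### The exploratory exposure-response regression (SAP 9.1.2) reports its effect for the wrong concentration step, leaves its starting model unclear, and makes no provision for few failures

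*SAP*

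**What the plan says.** The exposure and antiviral activity analysis in SAP 9.1.2 models the Week 48 Snapshot outcome of HIV-1 RNA at or above 50 c/mL by logistic regression. Appendix 13 (section 13.13.13) restricts the PK/PD displays to the Q4W arm. Section 2.2 lists the objective as exploratory.

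- **Scale.** Section 9.1.2: "The last trough and Week-8 trough PK concentrations will be logarithmically transformed with base of 2". Section 5.4.2 gives the reason: "for assessing the effect, one unit increase of the point estimate of" log2 concentration is to be read as a doubling on the original scale.
- **Reported effect.** Section 9.1.2, under the presentation of results: "Estimated effect represents the change in log odds for a two-unit increase in the pk concentration".
- **Candidates.** The randomisation strata (sex at birth, third agent class) and age, then "race, baseline CD4, baseline viral load, and baseline CDC subgroups", and then "last CAB/RPV trough concentration, CAB/RPV trough concentration at nominal visit of Week 8, Baseline BMI, length of injection needle".
- **Selection.** Each covariate is first fitted alone. The multivariate model is described as built from covariates with univariate P below 0.15. A later sentence in the same block opens the backward search with every covariate included, and the procedure is to "remove a covariate with the largest p-value (i.e. the least statistically significant) each time" until all that remain have p below 15%.

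No penalised or exact fit, rule for separation, or limit on the number of terms is given.

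**The concern.** Two of the SAP's instructions disagree about what the coefficient means, and the one governing the output is the wrong one. A reader of the table would attach the odds ratio to a step in concentration that the model did not estimate.

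The selection procedure also has two possible starting points, so two programmers could fit different models from the same text. Either start is fragile when failures are rare. A category with no failures gives an infinite maximum-likelihood odds ratio, and a 0.15 threshold applied to a long list readily admits chance associations. The stated aim of the multivariate step is to find covariates that may affect virologic response, so its output is open to being quoted as a list of predictors of failure on the long-acting regimen.

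**Working it through.** **1. Unit of the effect.** Let x = log2(C), with logit(p) = a + b·x. Raising x by 1 multiplies C by 2, so exp(b) is the odds ratio per doubling. Take an illustrative odds ratio of 0.50 per doubling and try each reading of the 9.1.2 label:

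| Reading | Change in C | Odds ratio |
|---|---|---|
| two-fold (as 5.4.2) | ×2 | 0.50 |
| two log2 units | ×4 | 0.50² = 0.25 |
| two raw units from C = 1 | 1 to 3 | 1/3 = 0.33 |
| two raw units from C = 5 | 5 to 7 | 5/7 = 0.71 |
| two raw units from C = 50 | 50 to 52 | 50/52 = 0.96 |

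The raw-unit rows use C/(C+2), which holds because the odds ratio per doubling is 0.50. The starting values are illustrative. Only the two-fold reading matches the fitted coefficient. A raw two-unit step has no single odds ratio in this model.

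**2. Candidate list.** Degrees of freedom from the categories in 5.4.2:

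- Strata, demographic and baseline: sex 1, third agent class 2, age 1, race 1, CD4 3, viral load 1, CDC stage 2. Total 11, from 7 covariates.
- PK/PD: last and Week 8 troughs for two drugs 4, BMI 1, needle length 1. Total 6, from 6 covariates.

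Together there are 13 covariates and 17 degrees of freedom (18 if both race codings are used), plus the intercept.

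**3. Subjects and failures.** Section 2.3 gives 570 randomised 1:1, so 570/2 = 285 on Q4W. As a check, recomputing Table 22 with 143 per arm at the interim and 285 per arm at the end reproduces all 32 cells in the rows for 0, 3, 5 and 8 comparator failures (for example 17.3, 57.3 and 13.3).

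The SAP gives no expected failure rate. Over an assumed range:

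| Rate | Failures of 285 | Failures per candidate df |
|---|---|---|
| 2% | 5.7 | 5.7/17 = 0.3 |
| 5% | 14.25 | 14.25/17 = 0.8 |
| 10% | 28.5 | 28.5/17 = 1.7 |

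The columns of Table 22 run from 5% to 10% on CAB LA + RPV LA, so 10% is the top of the range the SAP itself displays.

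**4. Selection when no covariate has any effect.** The simulation used 285 subjects, 300 runs per setting, the univariate filter at 0.15, then backward Wald selection at 0.15. Fits that did not converge in the univariate step did not pass the filter. Assumed prevalences were: sex 33%; third agent class 17/33/50%; age 25%; race 33%; CD4 5/10/20/65%; viral load 3%; CDC 65/30/5%; BMI 20%; needle 20%. Troughs were normal on the log scale, with correlation 0.6 within drug.

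| Failures | Mean df passing filter | At least one false predictor kept | Separation or non-convergence if all 17 df entered |
|---|---|---|---|
| 5 | 1.15 | 67% | 100% |
| 8 | 1.4 | 69% | 100% |
| 12 | 1.33 | 69% | 97% |
| 16 | 1.7 | 76% | 90% |
| 28 | 2.02 | 82% | 73% |

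The simulation error on a proportion near 70% is about √(0.7×0.3/300) = 0.026.

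The choice of starting set therefore matters. From the filtered set the models are small (at most 7 df in any run), though usually with a false member. From the full list the fit mostly fails.

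**The case against.** The strongest reply is that this is an exploratory analysis with a slip in its label. Section 9.1.2 itself states the base-2 transformation, 5.4.2 states the correct reading, and the label is most naturally a slip for two-fold. That stands as to the numbers: nothing estimated changes. It does not remove the need to correct a sentence that governs how results are presented.

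The filtered set is also the more natural reading of the selection text, since the sentence defining the multivariate variables comes first. That is fair, and it limits the separation problem. A reader might infer that the plan fits 17 parameters to at most about 16 failures. The documents do not support this: 17 is the candidate pool, and 16 is not a ceiling. That count needs non-inferiority to be met and about 9 control failures (3.2%); with 14 control failures, up to 20 on Q4W would still be non-inferior.

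Appendix 10 says PK/PD methodology will be in a separate document, so a rule for sparse data may exist there. It cannot be assumed, because 9.1.2 already sets out the model and selection in full. Section 5.4.2 allows small subgroups to be redefined before unblinding, but that rule looks at numbers of subjects, not failures.

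A reader might also infer that the lowest exposures will drop out because zero has no logarithm. Section 13.6.5 says that values below quantification ("NQ) will be imputed as zero for summary statistics") are handled this way only for summaries, and 9.1.2 says the data stay as observed. How such values enter this model is unstated, and loss of those subjects is not established.

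**Conclusion.** The effect label is wrong on both the raw and the log2 scale and contradicts 5.4.2. This is certain and needs no assumption. The starting set for backward selection is stated in two ways.

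The sparse-data risk is likely, not certain. It rests on assumed failure rates of about 2% to 10% and assumed covariate prevalences, and on reading plain logistic regression as ordinary maximum likelihood. On those terms, 67% to 82% of null analyses keep at least one false predictor, and a joint fit of all candidates fails in 73% to 100%.

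Two stronger statements should not be drawn. That the predictors found will be spurious goes too far: roughly a fifth to a third of null runs kept none, and real effects were not simulated. The figure 1 − 0.85^13 = 0.88 is the chance that at least one of 13 independent null covariates passes the first filter. It is not the chance that one is retained, and these covariates are not independent. Nor does the point touch the primary or key secondary conclusions, which do not use this model.

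**What to change.** In SAP 9.1.2:

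1. Replace the effect label with: *the odds ratio is per doubling of trough concentration (one unit of log2 concentration)*.
2. State that backward selection starts from the covariates with univariate P below 0.15, and delete the competing sentence.
3. Fit the univariate and multivariate models by Firth penalised likelihood with profile-likelihood confidence intervals, so that a category without failures still gives a finite estimate.
4. Label the selected covariates as hypothesis-generating in the tables and report. Firth fitting deals with separation; it does not stop a 0.15 threshold from admitting chance covariates.

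The cost is a few sentences in the SAP and an option in the logistic procedure, with no new data. The downside is slight shrinkage of the estimates. Replacing the selection by a short pre-named model is a possible preference, but is not required for an exploratory analysis.

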10. HEALTH OUTCOMES ANALYSES

10.1. Endpoint / Variables

- Change from Week 5 in Dimension Scores and proportion of participants considering pain and local reactions following injection using PIN (Perception of iNjection Questionnaire),
- Change from Baseline in HR QoL,
- Change from Baseline in health status using SF-12,
- Change from Baseline in treatment acceptance using ACCEPT, Change from Week 4b in tolerability of injection,
- Change from baseline in total “treatment satisfaction” score, and individual item scores of the HIV Treatment Satisfaction Status Questionnaire (HIVTSQs).

10.2. Summary Measure

Mean treatment difference (Q4W – Current ART) at visits of interest through to Week 48 (i.e. the assessment visits detailed in [Table 7](#)).

10.3. Population of Interest

The primary health outcomes analyses will be based on the Intent-to-Treat Exposed population, unless otherwise specified.

10.4. Strategy for Intercurrent (Post-Randomization) Events

If a participant discontinues treatment prior to the timepoint of interest such that there is no evaluable on-treatment assessment for the timepoint of interest (see [Table 20](#) for definition of on-treatment), the data will be computed or imputed (see Section [13.6.6](#))

10.5. Statistical Analyses / Methods

[Table 7](#) provides an overview of the planned analyses. Details of the planned displays are provided in [Appendix 13: List of Data Displays](#) and will be based on GSK Data Standards and statistical principles.

Table 7 Overview of Planned Health Outcome Analyses

Endpoints	Absolute								Change from Baseline							
	Stats Analysis			Summary		Individual			Stats Analysis			Summary		Individual		
	T	F	L	T	F	F	L	T	F	L	T	F	F	L		
Perception of Injection (PIN) at Week 5, 41, 48, 96																
Individual Item Scores				Y			Y									
Domain of 'Bother from injection site reactions', 'Leg movement', 'Sleep', 'Acceptability'	Y ^[4]			Y			Y				Y					
Health-related quality of life (HATQoL) at baseline, wk24, 48, 96, withdrawal																
Individual Item Scores				Y			Y									
Subscale of Life satisfaction, HIV medication, and disclosure worries				Y			Y	Y	Y ^[1]		Y					
Health Status (SF-12) at Baseline, wk24, 48, 96)																
Individual Item Scores				Y			Y									
Total Score, Mental health component (MCS) and physical component summary (PCS) ^[2]				Y			Y	Y	Y ^[1]		Y					
Treatment Satisfaction Score (HIVTSQs) at Baseline, Week 4b, 24, 44, 96, withdrawal																
Individual Item Scores				Y			Y									
Individual Item Scores by subgroup ^[3]				Y												
Treatment Satisfaction Score				Y			Y	Y	Y ^[1]		Y					
Treatment Satisfaction Score Change (HIVTSQc) at 48, withdrawal																
Individual Item Scores	Y			Y			Y									
Treatment Satisfaction Score Change	Y			Y			Y									

Endpoints	Absolute								Change from Baseline							
	Stats Analysis			Summary		Individual			Stats Analysis			Summary		Individual		
	T	F	L	T	F	F	L	T	F	L	T	F	F	L		
Treatment Acceptance (ACCEPT) at Baseline, week 8, 24, 48, 96, withdrawal																
proportion of Individual item score				Y			Y									
Acceptance/General Dimension Score				Y			Y	Y	Y ^[1]		Y					
Tolerability of injection (NRS) at week 4b, week 5, 40, 41, 96 within Q4W IM arm																
proportion of Individual item score				Y			Y									
Tolerability Score (Q4W IM only)				Y			Y				Y					
Treatment Preference at Week 48 (for both treatment arms) and Week 96 (for Current ART only)																
Treatment: Monthly injection vs Daily oral ART				Y			Y									
Willingness to switch at Baseline (Q4W IM), and Week 52 (Current ART)																
Willingness to switch				Y			Y									

1. Line Plot of Adjusted Mean (95% CI) for each treatment arm, as well as the adjusted mean difference (95%CI) between the two treatment arms (if questionnaire was used for both arms during maintenance phase).
2. Component scores will be calculated form Computer Software purchased from QualityMetric.
3. Please refer to Section 5.4 (i.e. randomized strata, demographic and baseline subgroup)
4. Wilcoxon Signed -rank test for analysis of ‘Acceptance’ only with p-value reported

10.6. Planned Health Outcomes Statistical Analyses

Statistical Analyses
Endpoints
Change from Baseline in 
 ○ HIVTSQs total treatment satisfaction score at Week 4b, 24, 44 ○ ACCEPT general acceptance score at Week 8, 24, 48 ○ SF-12: Total Score, physical component summary(PCS) and mental component summary(MCS) at week 24, 48 ○ HATQoL (Life satisfaction, HIV medications, disclosure worries) at week 24, 48.
Model Specification

 • An analysis of covariance (ANCOVA) model will be used at each visit at Maintenance phase with covariates: treatment, age (<50, ≥ 50), baseline third agent class, sex at birth, and race (i.e. white, non-white) (as described in 5.4) and baseline score value (as a continuous

variable).
 
 Adjusted point estimates will be derived as LSMEAN S using the observed margins (OM) option within PROC MIXED in SAS. No adjustment for multiplicity will be applied as these analyses will be considered exploratory. Interactions between treatment and each of the covariates will not be assessed unless the exploratory subgroup analyses on the primary endpoint highlights significant interactions. In this situation, the interaction(s) of interest will be assessed and, if necessary, results will be reported in the clinical study report. Interactions between treatment and the baseline score will be investigated but not included in the model. If interactions are found to be significant, results might have to be presented separately by subgroup. No adjustment for multiplicity will be applied as these analyses will be considered exploratory.

Dataset
 
 LOCF dataset will be used.

Model Results Presentation
 
 Adjusted treatment difference (Q4W IM – Current ART), its 95% CI and the associated p-value. The interaction between treatment and the baseline score will be included in a footnote. Plots of adjusted mean change from baseline (95% CI) for each treatment group, and the adjusted mean difference (95%CI) between the two treatment arms from the model will be generated across visit.

Statistical Analyses

HIVTSQc
 
 Treatment Satisfaction Score (Change) at Week 48

Model Specification
 
 An analysis of variance (ANOVA) model will be used with covariates: treatment, age (<50, ≥ 50 years old), baseline third agent, sex at birth, and race (white, non-white) (as described in Section 5.4)

Dataset
 
 The observed case (OC) dataset uses only the data that is available at Week 48, with no imputation for missing values.

Model Results Presentation
 
 Adjusted means, 95% CI, and associated P value will be presented for the treatment difference (Q4W IM –Current ART). Adjusted point estimates will be derived as LSMEAN S using the observed margins (OM) option in modelling.

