		Baseline, Day 1	4A	4B ^b	5 ^b	8, 12, 16, 20	24	28, 32, 36, 40	41 ^b	44	48	52	56A	56B ^b	60	64, 72, 80, 88	68, 76, 84, 92			96	Every 4 Weeks After Week 96	Every 12 Weeks After Week 96
Renal, bone, marker analytes (blood/urine) ^p	X									X								X			X	
PBMCs ^q	X																	X			X	
Genetics sample ^r	X																					
Pharmacokinetics – CAB + RPV only																						
PK sampling ^s (S)=Storage only				X	X	X	X	X	X	X	X		X	X	S		X				X	S
Investigational Products																						
Oral CAB and Oral RPV Dispensation ^t	X	X									X	X										
IP accountability (Pill Counts)		X	X									X	X									

Procedure	Screening Visit ^a	Maintenance Phase										Extension Phase								Withdrawal	Follow-up Phase
		Baseline, Day 1	Week																		
			4A	4B ^b	5 ^b	8, 12, 16, 20	24	28, 32, 36, 40	41 ^b	44	48	52	56A	56B ^b	60	64, 72, 80, 88	68, 76, 84, 92	96	Every 4 Weeks After Week 96		
IM treatment administration ^u			X		X	X	X		X	X	X	X	X	X	X	X	X	X	X		
Patient Reported Outcomes^v																					
HAT-QoL (short-form)		X				X				X								X			X
SF-12		X				X				X								X			X
HIV TSQs		X		X		X				X								X			X
HIV TSQc ^w										X											X
ACCEPT		X				X				X								X			X
Reason for Switch ^x		X									X										
Preference ^y										X								X			

Procedure	Screening Visit ^a	Maintenance Phase											Extension Phase						Withdrawal	Follow-up Phase				
		Week																						
		Baseline, Day 1	4A	4B ^b	5 ^b	8, 12, 16, 20	24	28, 32, 36, 40	41 ^b	44	48	52	56A	56B ^b	60	64, 72, 80, 88	68, 76, 84, 92	96			Every 4 Weeks After Week 96	Every 12 Weeks After Week 96		
NRS ^z			X	X			X Wk40 only	X									X							
PIN				X				X		X							X						X	

Follow Up Visit: Conduct approximately 4 weeks after the last dose of IP. Required only if the participant has ongoing AEs or lab abnormalities at the last on-study visit. This visit may be conducted by telephone.

- a. Complete all Screening assessments within 35 days. Participants may begin the Maintenance Phase as soon as all Screening assessments are complete. Participants may be rescreened once and will be assigned a new participant number.
- b. Visits at Weeks 4b, 5, 41, and 56b are only for participants randomized to CAB LA + RPV LA or transitioning from current ART to CAB LA + RPV LA during the Maintenance or Extension Phase, respectively.
- c. Confirmation of eligibility to enter the Maintenance Phase, and eligibility to enter the Extension Phase.

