13.3.4.2. PIN/HATQoL/SF-12/HIVTSQs/HIVTSQc/ACCEPT/Treatment Preference

PIN, HATQoL, SF-12, HIVTSQs, HIVTSQc, ACCEPT, Treatment Preference, Willing to Switch questionnaire assessments will be assigned to analysis visits as follows:
 Baseline: Baseline will be defined as last available recorded value up to and including the date of first maintenance phase dose of study treatment.

Post-Baseline nominal visit: There will be no slotting for Post-baseline planned nominal visits (i.e. analysis visit =visit). The post-baseline planned nominal visits for each questionnaire are listed in [Table 14](#).

Withdrawal/unscheduled post-baseline visit at Maintenance phase (per [Table 17](#)) will be slotted per the following slotting steps:

- Identify the ‘last nominal visit’ with the HO assessment performed prior to the unscheduled/withdrawal visit to be slotted during the Maintenance phase
- The unscheduled/withdrawal visit will be slotted to the planned nominal visit subsequent to the ‘last nominal visit’ during the Maintenance phase

Example 1, for HATQoL, the post-baseline planned nominal visits are Week 24, 48, and 96. If a subject has the ‘last nominal visit’ (with HATQoL assessment) at Week 24 prior to withdrawal at Week 36, the withdrawal assessment will be slotted to the subsequent planned nominal visit of Week 48.

Example 2, for HATQoL, if there is unscheduled visit between Week 24 and Week 48. This unscheduled visit will be slotted to Week 48 per the rule. In this case, there are two assessments with analysis visit equal to Week 48 (i.e. the slotted value and the value at

original nominal week 48 visit). The original nominal value will be selected for summary per the rule below for multiple records.

Table 14 Planned Nominal Visit of Health Outcome Data at Maintenance phase

Endpoints	Day1	WK4B	WK5	WK8	WK24	Wk40	WK41	WK44	WK48	WK52
PIN (Q4W)			X				x		x	
HATQoL	x				x				X	
SF-12	x				x				x	
HIVTSQs	x	X			X			x		
HIVTSQc									x	
ACCEPT	x			x	x				x	
NRS (Q4W)		X	x			X	x			
Treatment preference									x	
Willing to switch	X (Q4W)									x (CAR)

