13.7.2.2. Handling of Missing data for Statistical Analysis

Element	Reporting Detail
Snapshot	
 In the Snapshot dataset, subjects without HIV-1 RNA data in the assessment window for the visit of interest (due to missing data or discontinuation of IP prior to the visit window) do not belong to 'HIV-1 RNA < 50 c/mL (or <200 c/mL)'. The nature of this missing data will be further classified in Snapshot summaries as either 'HIV-1 RNA ≥ 50' or 'No Virologic Data at Week X'; Appendix 11: Snapshot Algorithm Details for full details
LOCF	
 In the LOCF dataset, missing values will be carried forward from the previous, non-missing available on-treatment assessment. If the baseline value is missing any missing values until the first non-missing value will remain missing.
Lipid LOCF	
Baseline for Lipids LOCF Analyses:
 
 Last evaluable lipids assessment up to and including the start of IP, where 'evaluable' is defined as: Lipid modifying agents not taken within 12 weeks of the date of assessment and Lipids are collected in a fasting state. Subjects with unevaluable Baseline for Lipids (as defined above) will be excluded from this dataset.

Element	Reporting Detail
	
Post-Baseline:
 
 ● If subjects initiate serum lipid-lowering agents Post-baseline, then the last available fasted On-treatment lipid values prior to the initiation will be used in place of future, observed On-treatment values. ● Imputation at visits with observed on-treatment values will continue even if the subject discontinues the lipid-lowering agent. Missing assessments will not be imputed 
Analyses Evaluated with Lipid LOCF dataset:
 
This dataset will be used to summarize fasting lipids parameters in the following displays:
 
 ● Summary of Chemistry Values by visit ● Summary of Chemistry Change from Baseline by visit ● Summary of TC/HDL ratio Change from Baseline. ● All other displays of lipids (i.e. toxicity tables and NCEP tables) will use observed fasting data, without LOCF imputation

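### HIVTSQs is compared between arms at Week 4b, a visit that only the injection arm has, so that estimate and p-value are not a randomised comparison

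*SAP*

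**What the plan says.** Section 10.6 lists "HIVTSQs total treatment satisfaction score at Week 4b, 24, 44" among its change-from-baseline endpoints. It states that "An analysis of covariance (ANCOVA) model will be used at each visit at Maintenance phase", with treatment and the baseline score among the covariates, on the LOCF dataset. The output is the adjusted Q4W IM minus Current ART difference, "its 95% CI and the associated p-value".

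Section 10.2 defines the summary measure as that mean difference "at visits of interest through to Week 48 (i.e. the assessment visits detailed in" Table 7), and Table 7 has the row "Treatment Satisfaction Score (HIVTSQs) at Baseline, Week 4b, 24, 44, 96, withdrawal" with no restriction by arm. The results go into Table 7.24 (Section 13.13.9) and into Figures 7.1 and 7.2 (Section 13.13.10), which plot adjusted means and their difference over time.

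Footnote b to the schedule in Section 13.2.1 says: "Visits at Weeks 4b, 5, 41, and 56b are only for participants randomized to CAB LA + RPV LA", with a further clause for control participants who switch in the Extension Phase.

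For missing data, Section 13.7.2.2 says that "missing values will be carried forward from the previous, non-missing available on-treatment assessment". For withdrawal and unscheduled questionnaires, Section 13.3.4.2 says: "The unscheduled/withdrawal visit will be slotted to the planned nominal visit subsequent to the" last nominal visit at which the questionnaire was completed. The same section leaves planned nominal visits unslotted.

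**The concern.** A between-arm model needs a measurement in both arms. By footnote b, Current ART participants have no Week 4b visit during the Maintenance Phase, and because nominal visits are not re-windowed, another control visit near Week 4 cannot stand in for it. Whatever enters the model for Current ART at Week 4b is therefore either imputed or comes from a small, selected group.

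HIVTSQs also carries a key secondary superiority test at Week 44 (Section 5.5.2). An invalid difference with a p-value would be the earliest post-baseline point of the same time course, in the same table and figures, and could be read as early evidence of improved satisfaction.

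**Working it through.** The SAP gives no SD, effect size or power for HIVTSQs, so there is no planned figure to reproduce. The check is a reading of the rules, followed by a calculation on stated assumptions.

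**Step 1: what a control participant has at Week 4b.** In Table 14 the only HIVTSQs assessment before Week 4b is Day 1. There are two readings of the LOCF rule.

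- *Baseline carried forward.* The sentence after the LOCF rule keeps values missing until the first observed one only when baseline is missing. This implies that a present baseline is carried. The control score at Week 4b is then the Day 1 score, and the change is 0.
- *Strict on-treatment reading.* Under Tables 17 and 20 a Day 1 assessment belongs to the screening phase and is pre-treatment, so nothing is carried. Controls then have no Week 4b value.

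Under either reading there is one exception. A control participant whose last questionnaire was at Day 1 and who has a withdrawal or unscheduled one before Week 24 has it slotted to Week 4b, the next HIVTSQs visit in Table 14, even if it was completed near Week 20.

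**Step 2: size of the bias under the first reading.** Let d be the true treatment effect and c the change that both arms would show anyway. The injection arm's mean change is c + d and the control mean is set to 0. The estimate is (c + d) − 0 = c + d, so the bias is c.

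**Step 3: false-positive rate when d = 0.** Inputs: 570 participants randomised 1:1 (Section 2.3), so about 285 per arm. Assumptions not in the SAP: scores with SD 1, correlation r between baseline and follow-up, and ANCOVA on treatment and baseline only.

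With controls fixed at zero change, the common slope is the average of (r − 1) and 0. The average residual variance is (1 − r²)/2 + (1 − r)²/4.

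- At r = 0.5: 0.375 + 0.0625 = 0.4375, so SE = √(0.4375 × 2/285) = 0.055.
- Had both arms been measured: SE = √(0.75 × 2/285) = 0.073.

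The approximate rejection rate at two-sided 5% is Φ(c/SE − 1.96). For c = 0.1 this is Φ(0.1/0.0554 − 1.96) = Φ(−0.155) = 44%.

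Simulation (4,000 runs per scenario) gives:

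| Shared change c (SD) | Mean estimate (truth 0) | Rejection, r = 0.5 | Range, r = 0.3 to 0.7 | Rejection, r = 0.5, 5% of controls with a slotted real value |
|---|---|---|---|---|
| 0 | 0.00 | 5% | 4.5–5.4% | 5% |
| 0.1 | 0.10 | 44% | 36–62% | 39% |
| 0.2 | 0.20 | 95% | 88–99.6% | 93% |
| 0.3 | 0.30 | 100% | 99.8–100% | 99.9% |

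With both arms really measured, the same model rejects in 4.4% to 5.8% of runs in every no-effect scenario.

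**Step 4: a true effect is also misstated.** With d = 0.2 SD and r = 0.5, the mean estimate is 0.40 if both arms rise by 0.2 SD and 0.00 if both fall by 0.2 SD.

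**The case against.** **Control assessment at Week 4b may have been intended.** Table 14 tags PIN and NRS as Q4W only but leaves HIVTSQs untagged at Week 4b. Section 2.2 lists Week 4b under an objective that compares with current ART. This shows that the SAP contradicts itself; it does not override footnote b. Note 1 to Table 7 does not help, because it makes the difference plot depend on the questionnaire, not the visit, being used in both arms.

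**The zero change is not certain.** This stands. The LOCF wording is ambiguous, and Section 10.4 refers to Section 13.6.6, where the HIVTSQs text is redacted, so a special rule cannot be excluded. No imputation rule, however, can supply a control measurement that was not taken.

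**The analysis is exploratory.** This stands and limits the weight of the point. Section 10.6 calls these analyses exploratory, and Section 5.5.2 names only Week 44 for the key comparison.

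Three stronger readings are tempting but not supported:

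- *A reader might infer that the main harm is an interval about 29% too narrow, with an SE ratio of 0.71.* That follows from halving the variance without the baseline covariate that Section 10.6 includes. With it, the squared ratio is 1/2 + (1 − r)/[4(1 + r)], giving 0.80, 0.76 and 0.74 at assumed r = 0.3, 0.5 and 0.7. Rejection also stays near 5% when there is no shared change. The problem is bias.
- *A reader might infer that the Week 44 key secondary test is undermined.* Both arms are assessed at Week 44. A Week 4b score reaches it only for injection-arm participants with no later HIVTSQs at all, since a withdrawal questionnaire after Week 4b is slotted to Week 24. The SAP does not give their number. Oral lead-in is also part of the randomised regimen (treatment start date, Section 13.6.1), so this is an ordinary LOCF limitation.
- *A reader might infer that a mixed model for repeated measures must replace LOCF.* That is a separate choice and is not needed to correct Week 4b.

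**Conclusion.** The Week 4b between-arm HIVTSQs analysis is wrong as written. Section 10.6, Section 10.2 and Table 7 call for a contrast at a visit that footnote b denies to one arm. If baseline is carried forward, the estimate is the injection arm's own change. If it is not, the control side consists of a few slotted withdrawal or unscheduled questionnaires. Neither is a valid randomised comparison.

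The bias equals the change that controls would truly have shown. The false-positive rates of about 44% to 100% rest on carry-forward of baseline, an assumed shared change of 0.1 to 0.3 SD, r = 0.5 and 285 per arm; none of the SD-scale inputs comes from the SAP. The consequence is confined to one exploratory time point, its p-value and its point on two figures. It should be corrected before analysis, but it does not threaten a confirmatory conclusion.

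**What to change.** 1. In Section 10.6, delete Week 4b from the between-arm HIVTSQs ANCOVA, keeping Weeks 24 and 44. Align Section 10.2 and Table 7.24.
2. Remove Week 4b from Figure 7.1 (adjusted means) and Figure 7.2 (difference). Present it as a within-arm summary for Q4W IM only.
3. Reconcile Table 7 and Table 14 with footnote b by marking HIVTSQs at Week 4b as Q4W only.
4. In Section 13.3.4.2, state that Current ART withdrawal or unscheduled HIVTSQs before Week 24 are slotted to Week 24, because Week 4b is not a planned visit for that arm.

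The cost is SAP wording and limited reprogramming of one analysis table and two figures. The slotting change may also alter the by-visit HIVTSQs summaries (Tables 7.18 to 7.23). No new data are needed, and the Week 44 model is unchanged.
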